2 OBJECTIVES

The objective of the study is to evaluate and compare the performance of the study TEST lens to the CONTROL lens, when worn on a daily disposable modality over a period of approximately one week each.

The primary outcome variable of this study is:

- Overall lens fit acceptance at the 1-week follow-up visit.

The secondary outcome variables are:

- Centration (optimal, slight decentration, moderate decentration but not encroaching limbus, excessive & occasionally encroaching limbus), collected at dispense & 1-week visit;
- Post-blink movement in primary gaze, mm, collected at dispense & 1-week visit;
- Push-up tightness in primary gaze (0-100), collected at dispense & 1-week visit.

Participants will be randomized to wear either the test or the control lens first. All lenses will be worn in a daily disposable lens wear modality for one week (-1/+3 days). The study involve up to 5 scheduled visits. The study design is shown in Figure 1.

[figure not shown]

Figure 1: Study Design, visits 1 & 2 may be on a single day, also visits 3 & 4 may be on a single day.

Visit 1: Includes screening, baseline assessments, fitting of both study lenses.

Visit 2: Dispense lens pair #1 (either test or control lens, randomized).

Visit 3: 1-week follow-up assessment of lens pair #1

Visit 4: Dispense of lens pair #2 (either test or control lens)

Visit 5: 1-week follow-up assessment of lens pair #2 and study exit.

- Participants will complete the following in-office subjective ratings on paper using a numeric rating scale (0 – 10) at visits 3 and 5 for each lens type:

- Lens handling;

- [Redacted]
- [Redacted]
- [Redacted]
- [Redacted]

[Redacted]

[Redacted]

[Redacted]

[Redacted]

- [Redacted]
- [Redacted]
- [Redacted]
- [Redacted]

- [REDACTED]
- [REDACTED]
- [REDACTED]
- [REDACTED]
- [REDACTED]

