5 STUDY POPULATION

5.1.1 SAMPLE SIZE CALCULATION

Sample size was calculated using the mean overall fit acceptance from the previous pilot BOXER study [REDACTED]

A sample size of 34 is recommended to detect a mean difference between lens Overall fit acceptance of 0.2 units on the 0 to 4 scale using a standard deviation of 0.4 with 80% power and alpha 0.05 in a two-tailed t-test. Therefore, it is recommended that at least 38 subjects are dispensed in the MIKI study, with a target of 34 to complete.

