5.1.2 NUMBER OF PARTICIPANTS

Participants will be screened using CORE records and advertising approved by the UW Office of Research Ethics. Approximately 38 participants will be dispensed with study products in the study, with a target of 34 completing the study.

A documented informed consent process will be conducted with all participants prior to their enrolment in the study and prior to any data collection or measurements.

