5.2 STUDY MATERIALS

5.2.1 LENSES

All study lenses are approved by Health Canada. They will be worn bilaterally, and on a daily disposable basis, therefore no lens care solution is required.

Table 1: Lens characteristics & parameter to be used in the study

	Test lens	Control lens
Manufacturer	CooperVision, Inc.	Alcon
Material	stenfilcon A	verofilcon a
HC licence #	91502	101910

Dk/t (barrer/cm)	100	100
Water content	54%	51%
Sphere power (D)	-2.00 to -5.00 (0.25 steps)	-2.00 to -5.00 (0.25 steps)
Base curve (mm)	8.4	8.3
Diameter	14.2	14.2
Replacement schedule	Daily disposable	Daily disposable

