5.3.3 DISPENSING LENS TYPE #1 (VISIT 2)

The procedures to be performed are outlined below:

1. The participant will be assigned a randomization ID (by the research assistant) and the first pair (lens pair #1) of contact lenses (either test or control lens) will be selected according to the randomization table.
2. Lens pair #1 will be provided to participants in a manner which does not unmask the participant or investigator, as described in Section 5.2.4.
3. The participant will insert the lenses.
4. The contact lenses will be allowed to settle for 10 minutes.
5. The participant will be asked to give subjective binocular ratings for:
 - a. [REDACTED]
6. [REDACTED]
7. [REDACTED]
8. Lens [REDACTED] fit will be assessed and graded according to the following grading scales:
 - a. [REDACTED]
 - b. [REDACTED]
 - c. Lens push-up tightness in primary gaze (0 – 100 scale);
 - d. Centration in primary gaze (scale: optimal, slight decentration, moderate decentration but not encroaching limbus, excessive & occasionally encroaching limbus);
 - e. Post-blink movement in primary gaze (mm);
 - f. Overall fit acceptance (0 – 4 scale, and reason if Grade 2 or less).
9. [REDACTED]

- b) [REDACTED]
 - c) Lens push-up tightness in primary gaze (0 – 100 scale);
 - d) Centration in primary gaze (scale: optimal, slight decentration, moderate decentration but not encroaching limbus, excessive & occasionally encroaching limbus);
 - e) Post-blink movement in primary gaze (mm);
 - f) Overall fit acceptance (0 – 4 scale and reason if Grade 2 or less).
6. Study lens collection at 1-week: investigator will remove study lenses from participant eyes while wearing a pair of disposable non-latex medical grade gloves. The lenses will be rinsed and stored according to sponsor instructions which will be provided at a later date. They will be labeled with study name, participant study ID, eye, visit# and date without any identifying characteristics. They will be stored in a -80 degrees centigrade freezer and shipped to the sponsor when all participants have completed the study.
 7. Slit lamp biomicroscopy assessments (see 5.3.2 for details).
 8. There will be a washout of 10 minutes after lens removal if Visit 4 is to be concurrent with this visit.

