5.3.5 DISPENSING LENS TYPE #2 (VISIT 4)

1. The participant will be assigned the second pair (lens pair #2) of contact lenses (either test or control lens), which will be selected according to the randomization table.
2. Lens pair #2 will be provided to participants in a manner, which does not unmask the participant or investigator, as described in Section 5.2.4.
3. The participant will insert the lenses.
4. The contact lenses will be allowed to settle for 10 minutes.
5. The same procedures will be followed as described in Section 5.3.3 DISPENSING LENS PAIR #1 (VISIT 2), points 5 to 11. [REDACTED]
6. The participant will be reminded to return for Visit 5 (1-week follow-up visit of study lens #2) and instructed to return used lens foils plus all leftover unworn lenses.

5.3.6 1-WEEK FOLLOW-UP OF LENS TYPE #2 (VISIT 5)

Participants will be asked to wear lenses for 6-8 hours prior to the visit. Participants who attend without wearing lenses for 6-8 hours will be rescheduled (unless they report problems when wearing the lenses).

1. The same procedures will be carried out as described in Section 5.3.4 1-WEEK FOLLOW-UP OF LENS TYPE #1 (VISIT 3), points 1 to 5.
2. Study lens collection at 1-week: investigator will remove study lenses from participant eyes while wearing a pair of disposable non-latex medical grade gloves. The lenses will be rinsed and stored according to sponsor instructions which will be provided at a later date. They will be labeled with study name, participant study ID, eye, visit# and date without any identifying characteristics. They will be stored in a -80 degrees centigrade freezer and shipped to the sponsor when all participants have completed the study.
3. [REDACTED]
4. [REDACTED]
[REDACTED]
[REDACTED]
[REDACTED]
5. [REDACTED]
 - [REDACTED]
 - [REDACTED]
 - [REDACTED]
 - [REDACTED]
 - [REDACTED]
 - [REDACTED]
 - [REDACTED]
 - [REDACTED]
 - [REDACTED]
 - [REDACTED]
 - [REDACTED]

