8.2 PROCEDURES FOR ADVERSE EVENTS

Treatment of an adverse event will depend on its nature and severity. Based on the clinical judgment of the investigator the participant may be referred to an ophthalmologist for treatment. The investigator will attempt to determine whether the reaction is related to the test device or a result of other factors. An adverse event form will be completed for each adverse event. If both eyes are involved, a separate adverse event form will be completed *for each eye*. Whenever possible, the adverse event will be photo-documented.

Expenses incurred for medical treatment as part of study participation will be paid by the sponsor (bills and prescription receipts kept). The participant must be followed until resolution or no further change is anticipated and/or referred for further care with the appropriate health care professional and/or recorded as being under appropriate health care as per investigator's discretion. A written report will be completed indicating the subsequent treatment and resolution of the condition.

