12 STATISTICAL ANALYSIS AND DATA MANAGEMENT

12.1 STATISTICAL ANALYSIS

Primary comparisons will be between study lenses, however there are some variables collected over time with the same lens and this time comparison will be analysed (e.g. 'at-home ratings on Days 1, 3 and 5).

All data will be analyzed by CORE at the University of Waterloo. Unmasked data analysis will be conducted using Statistica, SPSS, or other appropriate software. Descriptive statistics will be provided on information regarding baseline variables (age, gender, refractive error distribution, etc.). Table 6 lists the main outcome variables and anticipated statistical procedures. All data will be tested for normality of distribution using Shapiro-Wilk tests.

[figure not shown]

Table 6: Statistical analysis to be conducted

Variable	Analysis	Statistical test
Subjective ratings	Descriptive and other statistics	Mean, Median*, Standard Deviation, Minimum, Maximum, Frequency count
	Effect of treatment on outcome variable within subjects (comparison between study days) Effect of time on ratings (comparison over time)	Friedman Wilcoxon matched pairs test
[REDACTED]	Descriptive statistics	Mean, Median*, Standard Deviation, Minimum, Maximum, Count
	Effect of treatment on outcome variable within subjects (comparison between study days)	RMANOVA Paired t-test

* For non-parametric data only

The critical alpha level for statistical significance will be set at 0.05, with no adjustments for multiple comparisons.

All participants who were evaluated will be included in the analysis, unless their removal is agreed by the sponsor due to protocol deviations and/or adverse events. In the event of missing data, individual data points will not be extrapolated from the collected data.

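### Does the plan need a stated rule for combining the two eyes, and a label on the SD of 0.4, before the fit outcomes can be analysed?

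*Combined protocol and SAP*

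**What the plan says.** The primary outcome in section 2 is "Overall lens fit acceptance at the 1-week follow-up visit". The secondary outcomes are centration, post-blink movement and push-up tightness. Section 5.2.1 says of the study lenses: "They will be worn bilaterally, and on a daily disposable basis". The grading step in section 5.3.3 reads "Overall fit acceptance (0 – 4 scale, and reason if Grade 2 or less" and names no eye, whereas the subjective ratings in the same section are described as binocular.

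Elsewhere the protocol does work at eye level. Under section 5.3.6, on the collected lenses: "They will be labeled with study name, participant study ID, eye, visit# and date without any identifying characteristics". Section 8.2 says: "If both eyes are involved, a separate adverse event form will be completed".

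Section 5.1.1 sizes the study for a difference of 0.2 on the 0 to 4 scale, "using a standard deviation of 0.4 with 80% power and alpha 0.05 in a two-tailed t-test". It arrives at 34 and plans to dispense to 38 subjects. Section 5.1.2 repeats the figures as participants, "with a target of 34 completing the study". Table 6 in section 12.1 gives, for a row whose variable name is redacted, "Effect of treatment on outcome variable within subjects (comparison between study days", with repeated-measures ANOVA and a paired t-test. The same analysis description appears in the subjective-ratings row.

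**The concern.** Two eyes per participant can give two fit grades per lens and visit, and the two grades are likely to be correlated. The visible text leaves open whether the analyst uses one eye, the mean, the worse eye or both. Section 12.1 also says the analysis will be unmasked and calls the procedures anticipated, so the choice could in principle be made after lens-labelled data are seen.

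Two things would be at stake. Entering eyes as independent rows would make the nominal 5% test too liberal. Analysing one eye, if 0.4 came from two-eye means, would leave the study short of 80% power. For the four-category centration grade, the choice of rule also changes what is estimated. The protocol's care about eye in other places makes its silence on the fit outcomes more noticeable.

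**Working it through.** **Inputs from the documents.** Difference 0.2, SD 0.4, two-sided alpha 0.05, power 80%, n = 34 (section 5.1.1); 34 completing participants (section 5.1.2). **Assumed, because the documents give none:** the correlation ρ between the two eyes' between-lens differences, taken as 0.3, 0.5 and 0.8, with equal SD in both eyes.

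**1. Reproduce 34.** Take one between-lens difference per participant with SD 0.4. The noncentrality is (0.2/0.4) × √34 = 2.92 on 33 degrees of freedom. The noncentral t gives power 80.8% at n = 34 and 79.5% at n = 33. So 34 is the smallest sufficient n, and it counts participants with one value each.

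**2. Does the level of the SD matter if the two-eye mean is analysed?** SD of the mean = per-eye SD × √((1+ρ)/2).

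| ρ | SD of mean if 0.4 is per eye | Power, mean of eyes, n = 34 | One-eye SD if 0.4 is for the mean | Power, one eye, n = 34 | n for 80%, one eye |
|---|---|---|---|---|---|
| 0.3 | 0.322 | 93.9% | 0.496 | 62.6% | 51 |
| 0.5 | 0.346 | 90.4% | 0.462 | 68.8% | 44 |
| 0.8 | 0.379 | 84.7% | 0.422 | 76.6% | 37 |

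If 0.4 already refers to the two-eye mean and the mean is analysed, power is 80.8%. If 0.4 is per eye and one eye is analysed, power is also 80.8%. Only one mismatch loses power: a two-eye SD followed by a one-eye analysis.

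**3. Eyes as independent rows.** With 68 eyes from 34 participants in a paired t-test, simulation (200,000 null trials, normal data) gives a type I error of 8.6%, 11.0% and 14.8% at ρ = 0.3, 0.5 and 0.8. The large-sample formula 2 × (1 − Φ(1.96/√(1+ρ))) gives 8.6%, 11.0% and 14.4%. The 10% mark is passed at ρ of about 0.42. The simulation does not cover centration.

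**4. What 0.4 measures.** Steps 1 and 2 take 0.4 as the SD of the between-lens difference. Section 5.1.1 does not say so. If it were the SD of scores on a single lens, with correlation r between a participant's scores on the two lenses, the SD of the difference would be 0.4 × √(2(1−r)). That is 0.566, 0.473 and 0.400 at assumed r = 0, 0.3 and 0.5, with power at n = 34 of 51.7%, 66.7% and 80.8%. Exact reproduction of 34 as a paired calculation shows that 0.4 was used as the SD of the difference. It does not show where the value came from.

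**5. What the visible text can show.** Redactions fall on the pilot-study details in section 5.1.1, the opening words and first two items of the grading step in section 5.3.3, parts of the trial-fitting steps at Visit 1, all of section 5.5, and the variable name in Table 6. A figure before Table 6 is also not reproduced. An eye rule, or the definition of the SD, could sit in any of these.

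**The case for a change.** The strongest case for a change is that a participant-level analysis still leaves one eye, the mean and the worse eye open, that these differ in power or in what they estimate, and that a sentence fixed in advance costs nothing. With unmasked analysis and no multiplicity adjustment, an open choice on the primary outcome is not ideal. Redaction does not fully answer this, because the visible body of section 12.1, where a reader would look first, has no eye rule.

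Part of this stands. The visible text does lack the rule and does not label 0.4, and a line confirming both would be welcome. But the argument shows no stated rule or figure to be wrong. The inflated error rates belong to an analysis the plan does not propose and which its within-subject wording points away from. The power loss needs a particular mismatch between the pilot SD and the analysis, and nothing visible indicates it. Nor is the two-eye mean the only defensible choice: it matches a model clustered on participant only when both eyes' data are complete and balanced, and one eye named in advance would also be valid.

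**Conclusion.** No change to the plan follows. The within-subject wording, the target counted in completing participants and the exact reproduction of 34 from one paired difference per participant all point to the participant as the unit. An analyst would ordinarily reduce the two eyes to one value or account for the pairing. If 0.4 is the SD of the between-lens difference and the two eyes have equal SD, the two-eye mean gives at least 80.8% power at 34, whichever eye level 0.4 refers to.

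That assurance is conditional. If 0.4 is a single-lens SD, power could be as low as about 52% with uncorrelated lens scores, and the redacted pilot details in section 5.1.1 prevent checking this. The type I error of 8.6% to 14.8% applies only if eyes were treated as independent, at correlations that are themselves assumed. What remains is a low-priority clarification: how two eyes become one value, centration included, and what 0.4 measures. No error in n = 34 or in the stated analysis is shown.

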4.1.3 RANDOMIZATION

A randomization schedule will be generated using a web-based program: (for example www.randomization.com) by CORE's Data management team, and provided to the research assistants for the study. The schedule will determine the order of lens wear for participants in the study. Study investigators will remain masked to the randomization schedule until the study is completed and the database has been locked.

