5.3 SCHEDULED AND UNSCHEDULED VISITS

This study has 5 visits. The visits are as follows:

- **Visit 1:** Screening, baseline assessments, fitting of both study lenses.
- **Visit 2:** Dispense lens type #1 (normally combined with Visit 1)
- **Visit 3:** 1-week follow-up assessment of lens type #1 (6 to 10 days after Visit 2), worn lens collection
- **Visit 4:** Dispense of lens type #2 (normally combined with Visit 3)
- **Visit 5:** 1-week follow-up assessment of lens type #2 and study exit (6 to 10 days after Visit 4), worn lens collection

A scheduled follow-up visit may only take place when the participant attends wearing the study lenses for 6-8 hours. If this is not the case and the participant is not experiencing any problems with the lenses, the appointment will be rescheduled, ideally within the visit window.

Visits that fall outside of the specified visit windows will be designated as protocol deviations and at the end of the study, the data collected during protocol deviations will be assessed for their suitability to be included in the analysis population.

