8 ADVERSE EVENTS

See CORE SOP012_v02 for a description of all adverse events, including management and reporting. An 'adverse event' refers to any undesirable clinical occurrence in a participant, whether

it is considered to be device-related or not. Adverse events (AE) may be classified as ‘unanticipated adverse device effects,’ ‘serious adverse events,’ ‘significant adverse events,’ or ‘non-significant adverse events,’ as defined below, Table 4.

A number of conditions may result in temporary suspension until resolution. These include corneal infiltrates, corneal staining, limbal injection, bulbar injection or tarsal conjunctival abnormalities.

Table 4: Classification of types of adverse event

Classification	Definition
Serious Adverse Event	Those events that are life-threatening, or result in permanent impairment of a body function, or permanent damage to a body structure or necessitate medical (therapeutic) or surgical intervention to preclude permanent impairment of a body function or permanent damage to a body structure.
Significant Adverse Event	Those non-serious adverse events that occur with contact lens usage that are not sight-threatening but are usually symptomatic and may warrant therapeutic management and /or temporary or permanent discontinuation of contact lens wear.
Non-Significant Adverse Events	Those less severe non-serious adverse events that occur with contact lens usage that are not sight-threatening, may or may not be symptomatic and may warrant palliative management, such as ocular lubricants or temporary interruption of contact lens wear.
Unanticipated Adverse Device Effect	Adverse events in a study that were not previously identified in the protocol in terms of nature, severity, or degree of incidence. An Unanticipated Serious Adverse Device Effect is an unanticipated adverse event that is serious in nature and caused by or associated with the device and is considered reportable.

AE classification, coding (for reporting to the sponsor) and reporting details, plus examples, are provided in Table 5.

Table 5: Contact lens adverse event classification, coding and reporting guide

Code	Condition	Reporting
Serious Adverse Events		
01	Presumed infectious keratitis or infectious corneal ulcer	For all serious AEs: Notify sponsor as soon as possible, within 24 hours;
02	Permanent loss of ≥ 2 lines of best spectacle corrected visual acuity (BSCVA)	
03	Corneal injury that results in permanent opacification within central cornea (6mm)	

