12.2 DATA MANAGEMENT

Data from this study will be retained by CORE for a minimum of 25 years on a password-protected server. After 25 years, data will be disposed of in accordance with the guidelines laid out by the University of Waterloo.

At the completion of the study CORE will provide a copy of the study data to the sponsor when requested. All data will typically be sent using a secure file share system operated by the University of Waterloo called Sendit which uses 128bit (or 256bit) SSL encryption. This system provides a secure way to transfer files when email is not appropriate, whether because of file size, file type or concerns over security. Sendit includes features such as password protection, a restricted time period for download, IP logging and email notification of download. Files may be encrypted prior to transmission at the request of the sponsor. Using this method means that data files are only stored on University of Waterloo servers until they are downloaded by the sponsor.

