15.4.2 MINOR PROTOCOL DEVIATIONS

Protocol deviations caused by or which originate with research participants are considered minor, and normally are not reported to the ORE unless these result in increased risk to the participant(s). The following are examples of protocol deviations that are considered minor and do not require reporting to the ORE:

- Logistical or administrative aspects of the study (e.g., study participant missed appointment, change in appointment date);
- Inadvertent deviation in specific research intervention procedures or timing of the research intervention which would not impact upon the safety or efficacy of the study-related intervention or upon the experimental design (i.e., missing a measurement during a session that is not considered critical for the study).

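### Section 12.1 allows evaluated participants to be removed from an unmasked analysis with the sponsor's agreement, without criteria, timing relative to unmasking, a list of removals or an all-evaluated result

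*Combined protocol and SAP*

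**What the plan says.** Section 12.1 makes inclusion of all evaluated participants the default, and allows an exception: they are included "unless their removal is agreed by the sponsor due to protocol deviations and/or adverse events". The same section states: "Unmasked data analysis will be conducted using Statistica, SPSS, or other appropriate software".

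The two grounds are broad as the protocol defines them. Section 8 defines an adverse event as "any undesirable clinical occurrence in a participant", whether or not it is device-related. Section 15.4 divides deviations into major and minor, and the minor examples in 15.4.2 include "Logistical or administrative aspects of the study (e.g., study participant missed appointment, change in appointment date". Section 12.1 does not limit removal to major deviations.

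On timing, 5.3 has a related but narrower rule. It counts out-of-window attendance as a deviation and says that, once the study ends, "the data collected during protocol deviations will be assessed for their suitability to be included in the analysis population". It gives no criteria and does not refer to lock or unmasking.

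On masking, 4.1.3 says: "Study investigators will remain masked to the randomization schedule until the study is completed and the database has been locked". It does not mention the sponsor or the analysts. On data access, 12.2 says: "At the completion of the study CORE will provide a copy of the study data to the sponsor when requested".

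On reporting, deviations (section 6 and 15.4.3), adverse events (8.3) and discontinuations with reasons (section 9) must all be reported, and Table 6 lists counts among the descriptive statistics. Section 9 also lets a participant who chooses to discontinue withdraw their data from the analysis.

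**The concern.** Adverse events and protocol deviations happen after randomisation, and either can be a consequence of the lens being worn. In this crossover, removing a participant removes both lenses' grades. The paired comparison stays unbiased if removal is unrelated to the participant's between-lens difference in fit grade. If it is related, the result moves away from the lens that did better in the removed participants.

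The agreeing party also has an interest. Section 1 names the maker of the TEST lens. Section 5.2.5 sends the collected lenses to that company, and 5.3.6 sends them to the sponsor. The inference is that the sponsor makes the TEST lens. What is at stake is whether a reader of the primary result can be confident that the analysed set was fixed without knowledge of the outcome.

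**Working it through.** **1. Which safeguards are present for the 12.1 decision?**

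| Safeguard | Visible text |
|---|---|
| Grounds named | Yes, two (12.1) |
| Criteria within the grounds | None |
| Timing | 5.3 only: out-of-window data, at study end, no link to lock or unmasking |
| Masking of whoever agrees | None; 4.1.3 covers study investigators |
| Decision before data can go to the sponsor | Not required (12.2) |
| Underlying events reported | Yes (section 6, 8.3, section 9, 15.4.3) |
| List of participants removed from analysis | Not required |
| Result with removals restored | Not required |

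**2. Reproducing the plan's sample size.** Inputs from 5.1.1: difference 0.2, SD 0.4, two-sided alpha 0.05, power 80%. Taking 0.4 as the SD of the within-participant difference, the paired t-test has noncentrality (0.2/0.4)·√n. The smallest n with at least 80% power is 34 (power 0.808; n = 33 gives 0.795). A two-sample reading needs 63 per group, so the paired reading is the one that reproduces the plan.

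**3. Illustrating the size.** The documents give no rate of events or removals, so everything added here is an assumption: no true difference, m participants with a qualifying event that is itself unrelated to fit, and k of them removed. With 38 evaluated and normally distributed differences, 200,000 simulated trials per case give these rates of significant results in the favoured direction (nominal 2.5%) when the k least favourable of the m are always the ones removed:

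| m | k=1 | k=2 | k=3 | k=4 |
|---|---|---|---|---|
| 4 | 3.7% | 3.9% | 3.5% | 2.5% |
| 6 | 4.0% | 5.1% | 5.3% | 4.8% |
| 8 | 4.4% | 5.8% | 6.7% | 6.8% |

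Simulation error is about 0.1 percentage point. With 34 evaluated the maximum is 7.2%.

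Weaker selection gives less:
- Removal among the m unrelated to fit: about 2.5%.
- m = 6, choice correlated 0.3 with unfavourable fit: 2.9% to 3.2%. Correlated 0.5: 3.2% to 3.7%.
- Events themselves correlated 0.3 with unfavourable fit, and all 1 to 4 such participants removed: 3.3% to 5.4%.

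**4. Mean shift.** With no true difference, removing k participants whose average difference is −d moves the expected mean of the rest by k·d/(n − k). The largest simulated shift at n = 38 (m = 8, k = 4) is 0.034, which is 0.034/0.2 = 17% of the target difference. It corresponds to d = 0.034 × 34/4 = 0.29 units.

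**5. Sensitivity to the grading step.** The 0 to 4 scale's step is not stated. If grades are whole numbers, take differences of −1, 0 and +1 with probabilities 0.08, 0.84 and 0.08 (an assumption; SD = √0.16 = 0.4). The maximum at n = 38 is then about 4.2%. The shift can be checked by hand: 8 × 0.08 = 0.64 expected differences of −1 among the eight, and 0.64/34 = 0.019.

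**The case against.** The strongest reply is that the sentence restricts removal as much as it permits it. Inclusion is the default, only two grounds are allowed, and CORE, not the sponsor, analyses the data. No passage says that the sponsor proposes removals. The status reports in section 14 list deviations and adverse events but not fit grades. Because the underlying events must be reported and counts are tabulated, a reader could often tell that evaluated participants are missing. Section 15.7 also cites a data-management SOP that is not among the documents, and redacted text may hold more.

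Most of this stands, and it limits the point. A reader might infer that the sponsor can drop whichever participants of all 38 look worst for its lens. The documents do not support that: removal needs a deviation or an adverse event, and no passage describes the sponsor seeing grades before agreeing. A reader might also infer that removals would be invisible, which goes too far given the event listings and counts.

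What the reply does not answer is the order of events. Nothing prevents data from reaching the sponsor under 12.2 before removals are agreed. Event listings and counts also do not show who was removed from the analysis or how the result changed.

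**Conclusion.** The point holds as a missing procedure around a stated rule. No bias is demonstrated, and its direction and size cannot be derived from the documents. Under the illustrative assumptions, one-direction false positives run from about 2.5% (removal unrelated to fit) to about 6.8% (least favourable always chosen, normal differences), or about 4.2% with whole-number grades. The mean shift is at most 0.034, or 0.019 with whole-number grades. The upper figures need 8 of 38 participants to have qualifying events and deliberate choice among them. They rest on reading 0.4 as the SD of paired differences. The finding covers visible text only. It is worth correcting because it concerns the population for the primary comparison and is cheap to put right before unmasking.

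**What to change.** In 12.1, define the primary paired analysis as every randomised participant with a 1-week fit grade for both lenses, except those who withdraw their data under section 9. Delete adverse events and sponsor agreement as grounds for exclusion from it.

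Allow exclusions, including the out-of-window data in 5.3, only in a secondary analysis and only for major deviations specified in advance. Settle them without sight of lens identity or fit grades, before unmasking and before any data go to the sponsor under 12.2. List each exclusion with its reason, and report both results.

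The cost is wording in 12.1 and 5.3, one masked review and one extra table. No new staff role is needed. Planned power is not reduced: 80.8% with 34 complete pairs, 85.1% with 38. The downside is that a few noisy records stay in the primary analysis.
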